6.3.6 Removal of participants

Stopping Rules

Discontinuation of participants:

Participants for whom there has been at least 2 weeks without participant contact will be discontinued from the study. Exceptions may be made after discussions with the PIs, approval by the Medical Monitor, and consistency with the regulations of the Institutional Review Board/Ethics Committee (IRB/EC).

Discontinuation of study:

The study will be stopped if, in the judgment of the DSMB or the PI, there are sufficient safety concerns that arise during the conduct of the study that would indicate that participants are being harmed by the study interventions. Examples of such safety concerns would be:

-Other events that pose unacceptable risks to participants, e.g., multiple SAEs that are judged to be related to study interventions.

Withdrawal Rules

Discontinuation of Participants:

If a participant who does not meet enrollment criteria is enrolled, the study sponsor will be contacted. In such cases, the PI will provide information on the participant's anticipated benefit or current benefit from being enrolled in the study or continuing to receive study drug respectively. In addition, the PI will discontinue participants from the study drug or the study or both in the following circumstances:

- Participant has evidence of progressive disease.
- The participant, for any reason, requires treatment with another therapeutic agent that has been demonstrated to be effective for treatment of the study indication. In this case, discontinuation from the study occurs prior to introduction of the new agent.
- The PI decides that the participant should be withdrawn from the study. If a SAE or a clinically significant laboratory value is the basis for this decision, the PI will discontinue the study therapy and take appropriate measures. The PI will immediately notify the study sponsor or its designee.
- The participant or attending physician requests withdrawal of the participant from the study.
- The investigator or the study sponsor stops the study or stops the participant's participation in the study for medical, safety, regulatory, or other reasons consistent with applicable laws, regulations, and good clinical practice (GCP).

- The study therapies have shown unacceptable side effects.
- The participant is noncompliant with study procedures.
- In the clinical judgment of the investigator, the participant requires acute detoxification from the alcohol.

When a participant withdraws before completing the study, the reason for withdrawal will be documented in the CRF and in the source document.

6.4 Statistical Method

Descriptive statistics will be used to summarize the data set. Measures of central tendency and measures of variability will be reported for the chief variables of interest as noted below in 6.4.3.

6.4.1 Statistical Design

As this is a pilot feasibility study, no inferential statistics will be used.

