4.2 Primary Objective

As this is a small pilot study, the Primary Aims are *process*- rather than *outcome*-oriented:

1. To establish the feasibility and safety of giving alcohol to human participants in a laboratory alcohol self-administration procedure;
2. To establish the feasibility and safety of administering AABM training sessions; and
2. To allow our research team to gain experience with these procedures and fine-tune them.

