5.3.1 Number of Participants

The study will enroll 12 men participants. We anticipate needing to start up to 15 participants to get 12 to complete 2 human lab sessions and the majority of the 6 AABM training sessions.

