6.4.2 Sample Size Considerations

Not applicable.

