6.4.3.1 Primary Analyses

Primary analyses will consist of descriptive statistics. These measures of feasibility are:

1. Time needed to recruit, screen, and run the study procedures for 4 participants
2. Retention rates at the various timepoints in the study process (screening, Human Lab ADP session 1,2,3, and follow-up).

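### Retention and adverse-event rates from 12 to 15 men have no planned statement of precision, although the primary aims are to establish feasibility and safety

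*Combined protocol and SAP*

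**What the plan says.** Section 4.2 gives two primary aims that bear on this point: "To establish the feasibility and safety of giving alcohol to human participants in a laboratory alcohol self-administration procedure" and "To establish the feasibility and safety of administering AABM training sessions". Its introduction says that, in a small pilot, these aims concern process and not outcome.

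Section 5.3.1 sets the size: "The study will enroll 12 men participants", followed by "We anticipate needing to start up to 15 participants to get 12 to complete 2 human lab sessions". That sentence goes on to require most of the six training sessions as well. Section 6.4.2, on sample size, reads "Not applicable".

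On analysis, section 6.4.1 says "As this is a pilot feasibility study, no inferential statistics will be used" and section 6.4.3.1 says "Primary analyses will consist of descriptive statistics". One of the two primary measures is "Retention rates at the various timepoints in the study process"; the other is the time needed to run the study. Sections 6.4 and 6.4.3 plan summaries of average and spread, and section 6.4.3.3 plans descriptive summaries of adverse effects. No section gives a confidence interval, a confidence level, a precision target or a feasibility threshold.

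**The concern.** The aims and the analysis rule do not fit together. Establishing that a procedure is feasible and safe is a statement about what would happen in further participants. The planned output describes only the men observed. For continuous measures such as time, a standard deviation at least shows the spread. For a yes/no outcome such as retained or not, or event or no event, it adds nothing to the percentage.

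Section 2.1 says that the pilot data and the demonstration of feasibility are meant to support proposals for larger studies. Designers and funders of those studies will read the retention and adverse-event rates. A bare percentage retained, or a bare zero for serious adverse events, would not tell them how wide a range of true rates fits so few men. The study gives alcohol to heavy drinkers, so the zero-event case matters most.

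**Working it through.** **Is there a planned figure to reproduce?** No. There is no sample size calculation and no stated dropout rate. The only planning numbers are up to 15 started and 12 completing (section 5.3.1). They imply 12/15 = 80% completion if the ceiling of 15 is reached.

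**Inputs.** n = 12 and n = 15 from section 5.3.1. The 95% level and the example counts are assumptions of this review.

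**Does a measure of spread supply the precision?** For a proportion p, the standard deviation of the yes/no outcome is √(p(1 − p)). At p = 0.80 this is √(0.80 × 0.20) = 0.40, whatever the number of participants. It carries no information about precision beyond the rate itself.

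**Retention, exact (Clopper-Pearson) two-sided 95% interval.** For x of n, the lower limit is the 0.025 quantile of Beta(x, n − x + 1), and the upper limit is the 0.975 quantile of Beta(x + 1, n − x). When x = n the upper limit is 100%.

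| Completing / started | Rate | Exact 95% interval |
|---|---|---|
| 12/15 | 80% | 51.9% to 95.7% |
| 12/14 | 86% | 57% to 98% |
| 12/13 | 92% | 64% to 100% |
| 12/12 | 100% | 73.5% to 100% |

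The 12/15 interval is 95.7 − 51.9 = 43.8 percentage points wide. As a check by another method, the Wilson interval for 12/15 is 54.8% to 93.0%, which leads to the same conclusion.

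**Zero events.** The upper limit of the two-sided 95% interval is 1 − 0.025^(1/n); the one-sided 95% limit is 1 − 0.05^(1/n).

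| Events / men | Two-sided 95% upper limit | One-sided 95% upper limit |
|---|---|---|
| 0/12 | 1 − 0.025^(1/12) = 26.5% | 22.1% |
| 0/15 | 1 − 0.025^(1/15) = 21.8% | 18.1% |

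A single event would give an exact two-sided interval of 0.2% to 38.5% in 12 men and 0.2% to 31.9% in 15.

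**Chance of seeing no event when the risk is real.** This is (1 − p)^n. At a true risk of 10%, it is 0.90^12 = 28% in 12 men and 0.90^15 = 21% in 15. At 5%, it is 0.95^12 = 54% and 0.95^15 = 46%.

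**The case against.** The strongest reply is that a descriptive analysis is a stated and coherent choice for a pilot of 12 men. Section 4.2 frames its aims as process aims, one of which is simply for the team to gain experience. Section 6.2.1 says that this is not an efficacy study, and section 2.2.1 argues that pilots should test feasibility and not size a later trial. Intervals could also be added at write-up without changing conduct or data. All of this stands as a defence of having no hypothesis tests. It does not supply a precision statement for the rates, and an analyst who follows section 6.4.1 literally would leave the intervals out.

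Four stronger readings are tempting, and the documents do not support them:

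- **That the plan expressly forbids intervals.** It never mentions them. They are excluded only by implication, through a sentence that covers all inferential statistics.
- **That readers would have no sign at all of imprecision.** The sample size is plain and measures of spread are planned. A reader given the numerator and denominator could work out an interval, although the plan does not require both to be reported.
- **That 12 of 15 is the plan's target.** Fifteen is a ceiling, so 80% is the lowest completion rate provided for; 12 of 14 or 12 of 13 would fit the same sentence. It is used above only as an example.
- **That changes in drinks or craving should also have intervals.** Section 6.4.3.2 specifies no change estimate. If all men receive active training, as section 6.1.3 says, there is no control, and an interval for the pre-post change would act as a paired test and invite the efficacy reading that section 6.2.1 disclaims. Drinks are also limited to 0 to 8 per session, which makes a t-interval doubtful with 12 men.

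**Conclusion.** The point holds for proportions: retention at each step and adverse-event rates. The rule in section 6.4.1 leaves them without any planned statement of precision, and the imprecision is large. If 12 of 15 men complete, the data fit true completion rates from 52% to 96%. With no serious adverse events, true rates up to 26% (12 men) or 22% (15 men) are not excluded at two-sided 95%.

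This rests on reading a confidence interval as an inferential statistic, on the 95% level, and on denominators of 12 to 15. Retention at screening will have a larger denominator and a narrower interval.

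A reader might infer that the pilot is invalid or that its descriptive approach is wrong; neither follows. Nor would intervals alone establish feasibility, since the plan sets no threshold to compare them with. They would show what the pilot can and cannot support. This is a cheap improvement in reporting, not a flaw in the design.

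**What to change.** Replace the sentence in section 6.4.1 with:

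> No hypothesis tests will be done. Retention at each step and adverse-event rates will be reported as numerator/denominator with exact (Clopper-Pearson) 95% confidence intervals. The denominator is the participants who entered that step: those consented, for screening; those started, for ADP session 1 and later retention; those exposed to the procedure, for adverse events.

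Step-specific denominators are needed because a count of men started cannot serve for screening, and men who leave after the first laboratory session were never exposed to training. Keep drinks and craving descriptive, without t-intervals, and do not present 12 of 15 as a benchmark.

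The cost is one sentence and a few lines of output, with no change to visits, data or sample size. The downside is that the results will look less certain.

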6.4.2 Sample Size Considerations

Not applicable.

6.4.3 Planned Analyses

Descriptive statistics will be used to describe the data set. Measures of central tendency and measures of variability will be reported. Chief variables of interest are listed below in 6.4.3.1, 6.4.3.2, and 6.4.3.3.

6.4.3.1 Primary Analyses

Primary analyses will consist of descriptive statistics. These measures of feasibility are:

1. Time needed to recruit, screen, and run the study procedures for 4 participants
2. Retention rates at the various timepoints in the study process (screening, Human Lab ADP session 1,2,3, and follow-up).

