5.1.1 Study Duration

The study begins with a screening visit that is expected to last approximately 4 hours. If it is deemed safe for the participant to enroll in the study and they meet all eligibility criteria, then the participant will be scheduled for 2 human lab sessions, each 12 hours long. The human lab sessions will take place on Week 2 (1st human lab session) and Week 5 (2nd human lab session). After each human lab session, a study coordinator will conduct a phone visit which is estimated to take 10 minutes. In addition to the human lab sessions, participants will come to the Ft. Miley campus 3 times per week for 3 weeks to complete Alcohol Approach Bias Modification (AABM) training sessions. These computerized training sessions last 20-30 minutes and will occur during Weeks 3 and 4 of the study. A follow-up visit will be scheduled 7 days after the 2nd and final human lab session. In total, participants can expect to spend about 32 hours over the course of 6 weeks.

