5.2.1 Primary Outcome Variables

The primary outcome variables are measures of feasibility:

1. Time needed to recruit, screen, and run the study procedures for 12 participants.
2. Retention rates at the various in the study process (screening, Human Lab ADP session 1 + 2, AABM training sessions 1 – 6, and follow-up).

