6.2.1 Efficacy

This is a pilot feasibility study, not an efficacy study. The primary outcome variables are measures of feasibility:

1. Time needed to recruit, screen, and run the study procedures for 12 participants.
2. Retention rates at the various in the study process (screening, Human Lab ADP session 1 + 2, AABM/sham training sessions 1-6, and follow-up).

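### The planned primary analysis does not match the primary outcome: it counts 4 participants instead of 12, names a third drinking session that does not exist, and leaves all six training sessions out of retention

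*Combined protocol and SAP*

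**What the plan says.** **Aim.** The second primary aim in 4.2 is "To establish the feasibility and safety of administering AABM training sessions".

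**Primary outcome.** Section 5.2.1 sets two feasibility measures. The first is the time to "run the study procedures for 12 participants", with recruitment and screening included. The second is retention at "screening, Human Lab ADP session 1 + 2, AABM training sessions" 1 to 6, and follow-up. Section 6.2.1 repeats both, ending its retention list with "AABM/sham training sessions 1-6, and follow-up".

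**Primary analysis.** Section 6.4.3.1 gives item 1 as "Time needed to recruit, screen, and run the study procedures for 4 participants" and item 2 as "Retention rates at the various timepoints in the study process (screening, Human Lab ADP session 1,2,3, and follow-up". No training session appears.

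**Design.** Section 6, step (4), has two ADP sessions, one before and one after training. Sections 3.2, 5.1, 5.3 and 5.3.1 all give 12 participants. Sections 2.2.1, 3.2, 5.1 and 6, step (6), all give six training sessions over two weeks.

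**Outlying schedule text.** Section 5.1.1 has participants attend "3 times per week for 3 weeks to complete Alcohol Approach Bias Modification (AABM) training sessions", but also says these sessions "will occur during Weeks 3 and 4 of the study". The cognitive training paragraph of 6.3.5 spreads the six sessions over 3 weeks. ADP session 2 falls in Week 5 in 5.1.1 and in Week 4 in the 6.3.1 table. Section 6.3.5 also refers to a study of 11 weeks, a Timeline Followback (TLFB) at training session 8, and a neurocognitive battery at training session 9.

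**The concern.** The analysis section should report what the outcome section defines, and here it does not. Section 6.4.1 rules out inferential statistics, so the descriptive counts in 6.4.3.1 are the whole primary result. Section 6.4.3 sends the analyst to that list for the main variables.

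Followed as written, it would leave retention in the intervention under test out of the primary result. It would also leave out the information needed to count completers as 5.3.1 describes them, since that description requires most of the six training sessions as well as both lab sessions. The time measure would describe 4 participants in a study of 12.

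The schedule conflicts matter less. They leave staff with differing instructions on the length of the training course, the week of ADP session 2 and the sessions at which some measures are taken.

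**Working it through.** The plan has no calculation to reproduce: 6.4.2 says sample size is not applicable. The check is a count across sections.

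| Item | 5.2.1 and 6.2.1 (outcome) | 6.4.3.1 (analysis) |
|---|---|---|
| Participants for the time measure | 12 | 4 |
| Screening | 1 | 1 |
| ADP sessions | 2 | 3 |
| Training sessions | 6 | 0 |
| Follow-up | 1 | 1 |
| Retention points | 1 + 2 + 6 + 1 = 10 | 1 + 3 + 1 = 5 |

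- Section 6, step (4), has two ADP sessions, so 5 − 1 = 4 of the listed points exist in this design.
- Omitted points: 10 − 4 = 6, which are exactly the six training sessions.
- Time measure: 4/12 = one third of the planned sample.
- No other section supports 4 participants or a third ADP session. The secondary outcomes in 5.2.2 and 6.4.3.2 both refer to two ADP sessions.

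**Schedule (secondary).**

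- Section 5.1.1 read literally: 3 per week × 3 weeks = 9 attendances, against 6 sessions. With its own Weeks 3 and 4: 3 per week × 2 weeks = 6, which agrees with 2.2.1, 3.2, 5.1 and 6, step (6). The reference to 3 weeks is therefore the outlier, as it is in the cognitive training paragraph of 6.3.5.
- Total length: 6 weeks in 5.1.1, 5 in the 6.3.1 table and 11 in the TLFB entry of 6.3.5. The figure of 11 matches no schedule in the document.
- Training sessions 8 and 9 cannot occur in a six-session course. The visit table in 6.3.5 places the neurocognitive tasks at sessions 1 and 6.

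**The case against.** The strongest reply is that the error reveals itself. Nobody can report an ADP session 3 that does not take place, and the correct outcome is stated twice, with 12 participants and sessions 1 to 6. Training attendance would be on record in any case: 6.3.5 schedules adverse event and medication forms at every training session and pays by training visit, and under 7.4 the data and safety monitoring board reviews retention. With descriptive statistics only, no error rate or power changes.

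Most of that stands, and it limits the harm to reporting. It does not remove the defect. The false session 3 and the 4 participants are easy to spot, but the missing training sessions are not. Once session 3 is struck out, the remaining list reads as complete and still contains no training.

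On the schedule, a reader might infer more than the documents support:

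- *That the training calendar as a whole cannot be run.* Only the one sentence in 5.1.1 contradicts itself; four other sections agree on two weeks.
- *That one version compresses training into a single week.* This rests on the 6.3.1 table alone, and it is not certain how many rows its Week 3 label covers. The payment table in 6.3.5 pairs the sessions but gives no week numbers.
- *That the text is left over from a nine-session study.* Nine attendances and sessions 8 and 9 would fit such a course, and 2.2.1 mentions nine sessions as an option. The documents do not say so, and the correction is the same either way.

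**Conclusion.** The point holds as an internal inconsistency in the current text. The primary analysis covers 4 of 10 defined retention points, omits all 6 training sessions, adds 1 session that does not exist, and measures time for a third of the planned sample. It should be corrected before analysis.

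This rests on two readings. The first is that 5.2.1 and 6.2.1 state the intended outcome, which the aim in 4.2, the two-session design and the repeated target of 12 all support. The second is that the analyst works from 6.4.3.1, as 6.4.3 directs.

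A reader might conclude that feasibility data on the training would be lost. The documents do not support that: attendance would be recorded and could be counted under any of the schedules. The harm is an incomplete primary report. The references to sessions 8 and 9 also cost little, because the visit table places the neurocognitive tasks at session 6 and TLFB is also taken at the lab, phone and follow-up visits.

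**What to change.** **Primary.** In 6.4.3.1, change 4 participants to 12 in item 1. In item 2, list screening, ADP sessions 1 and 2, AABM training sessions 1 to 6, and follow-up.

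**Secondary.** Align the outlying schedule text with six sessions over two weeks:

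- Change 3 weeks to 2 weeks in 5.1.1 and in the cognitive training paragraph of 6.3.5.
- Remove the 11-week study length from the TLFB entry in 6.3.5.
- Reconcile the week of ADP session 2 between 5.1.1 (Week 5) and 6.3.1 (Week 4), with the follow-up week and total length to match. At the same time, state whether training sessions are attended singly, as 5.1.1 implies, or in pairs, as 6.3.1 and the payment table show.
- Set the neurocognitive battery at training sessions 1 and 6 throughout 6.3.5.
- Replace the session 8 TLFB with one at an existing session.

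The cost is amendment wording. No extra participants or procedures are needed. If the sponsor settles on single training visits, the paired rows in the payment table also need restating.

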6.4.3.2 Secondary Objectives Analyses

Descriptive statistics will be used to summarize the data set. The variables analyzed will include:

1. Alcohol craving
2. Alcohol consumption during each of the 2 Human Lab ADP sessions.
3. Alcohol – medication interaction effects on BAES and computer tasks (AAT, BART, and DD)

6.4.3.3 Safety

Descriptive statistics will be used to summarize the data. The SAFTEE will be used to assess adverse effects. Descriptive statistics will be used.

7. TRIAL ADMINISTRATION

7.1 Institutional Review Board (IRB) Review

The Human Research Protection Program (HRPP) reviews and monitors research involving human participants at UCSF and affiliate institutions to ensure the ethical and equitable treatment of the research participants. Within the HRPP, the Institutional Review Board (IRB) reviews all research that involves human participants performed by UCSF faculty.

7.2 Unanticipated Problems

[Explain how unanticipated problems that may occur during the study will be handled, communicated to the IRB, sponsor, and FDA, if applicable.]

7.3 Study Monitoring

Study monitoring will be conducted by the DSMB.

7.4 Data Safety Monitoring Plan

Plan to monitor study progress and safety: The Data and Safety Monitoring Plan (DSMB)

The DSMP for this project consists of:

- a Data and Safety Monitoring Board (DSMB)
- a schedule of DSMB meetings to review study data and events

- a list of study data and event items to be reviewed by the DSMB
- procedures for communicating DSMB findings to the CHR, the study sponsor (Department of Defense) and other appropriate entities
- a plan for conducting and reporting interim analysis
- stopping rules
- rules for withdrawing study participants from the study interventions

These elements of the DSMP are described below:

The Data and Safety Monitoring Board (DSMB)

The Data and Safety Monitoring Board (DSMB) is a group of 3 physicians who are not study investigators and who are experts in the area of clinical research and substance use disorders. The current composition of the PI's DSMB is: [name]., a clinical investigator and Medical Director, PTSD Clinic, SFVAMC; [name]. [medical Monitor], an experienced human clinical investigator, Assistant Professor of Psychiatry at University of California, San Francisco and [name]., Ph.D., an experienced basic neuroscience investigator and attending psychiatrist, SFVAMC.

The DSMB will meet biannually to review data reports prepared by the PI regarding the progress of the study and will monitor patient enrollment, retention, outcomes, adverse events, and other issues related to patient safety. The DSMB will make recommendations to the PI as to whether the study should continue or be modified or terminated. The DSMB can consider patient safety or other circumstances as grounds for early termination. Any member of the DSMB can ask for a meeting of the group if he/she feels that it is necessary, based upon the data.

During the course of the study, reports will be prepared and distributed to the Data and Safety Monitoring Board on a biannual basis. In order for the Data and Safety Monitoring Board to discharge their duties for overseeing the study and the rights of the patients, they will receive analyses of the primary outcome measures and the important secondary measures on a quarterly basis. The DSMB will receive reports of serious adverse events (SAEs) within 72 hours of their occurrence.

DSMB Minutes will be prepared by the Study Coordinator within 5 working days after each biannual DSMB meeting.

Medical Monitor

[name]., Medical Director of the PTSD Clinic at San Francisco VA Medical Center will serve as the Medical Monitor. As Medical Monitor, [name] will review all unanticipated problems involving risk to subjects or others, serious adverse events and all subject deaths associated with the protocol and provide an unbiased written report of the event. At a minimum, the medical monitor will comment on the outcomes of the event of problem and in case of a serious adverse event or death, comment on the relationship to participation in the study. The Medical Monitor will also indicate whether she concurs with the details of the report provided by the principal investigator. Reports for events determined by either the investigator or medical monitor to be possibly or definitely related to participation and reports of events resulting in death will be promptly forwarded to the IRB and other governing authorities.

